### MTD suggestion from the Bayesian two-parameter logistic regression model

The MTD as suggested from the modeling will be derived as follows:

- (1) The BLM will be updated with all DLT data (SMC decision) from the dose escalation.
- (2) The dose with targeted toxicity probability of 30% will be identified for each of the MCMC samples. The median of all the “30% doses” over the MCMC samples will be the fitted dose for MTD.

(3) The next lower tested dose with the upper bound of the one-sided 95% credible interval  $\leq 40\%$  and with estimated DLT probability  $\geq 17\%$  and  $\leq 30\%$  will be selected as suggested MTD.

(4) If none of the tested doses fulfill the criteria in 3), there is no MTD suggestion from the model.

This information from items (3) and (4) will be forwarded to the SMC that will decide on the determination of the MTD.

Additionally, the SMC will receive the estimated DLT probability and associated probability quantiles for all other doses tested.

The fitted dose with 30% DLT probability (from item (2)) and the two-sided 95% credibility interval will be tabulated.

For above analysis either SAS or R (using the package bcrm or crmPack) will be used.

#### Frequentist MTD suggestion

As second approach, the MTD as suggested by the frequentist estimation will also be derived:

(1) All DLT data from the dose escalation will be included in a two-parameter logistic regression model (intercept and slope over log of the scaled dose, no prior; if the model does not converge, it will be reported as not calculable; the program code for this analysis can be found in the TLF shells).

(2) The dose with targeted toxicity probability of 30% will be identified.

(3) The next lower tested dose will be selected as suggested MTD.

The fitted dose with 30% DLT probability (from item (2)) and the two-sided 95% confidence interval will be tabulated.

Additionally, a table will be produced, providing the estimated probability for DLT with a 95% confidence interval, based on the frequentist logistic model.

The models will be based on DLTs as identified by SMC.

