9.4.2 Safety Analyses

The DLT analysis will be performed on the DLT Analysis population. All other safety analyses will be performed on the Safety Analysis population. See [Table 17](#).

Table 17 Safety Analyses

Endpoint	Statistical Analysis Methods
Part 1A	
Primary	
DLT	
AEs classified as DLTs as assessed by SMC will be evaluated.
 
Bayesian dose toxicity analysis.
 
At primary analysis for Part 1A, the number and proportion of participants experiencing DLTs will be reported by dose level, based on observations during the first study intervention evaluation (21 days). Posterior probabilities (2.5%, 25%, 50%, 75%, and 97.5% quantiles) for DLT rates at selected doses will be estimated from the Bayesian dose toxicity model.
 
Sensitivity analysis using frequentist modeling (without prior).
 
Regarding intercurrent events: These are considered in the definition of DLTs and DLT analysis set.

Secondary	
AE	
AEs will be coded according to the latest available version of MedDRA. Severity of AEs will be graded using the NCI-CTCAE (Version 5.0). Missing classifications concerning study intervention relationships will be considered related to the study intervention. TEAEs are defined as AEs emerging or worsening after start of study intervention until 30 days after the end of study intervention period.
 
Following TEAEs will be presented in summaries by incidence and type according to MedDRA System Organ Classes and Preferred Terms:
 
 • TEAEs. • SAEs. • TEAEs related to study interventions. • NCI-CTCAE Grade 3 or higher TEAEs. • NCI-CTCAE Grade 3 or higher related TEAEs. • TEAEs leading to interruptions, dose modifications of study interventions. • TEAEs leading to permanent discontinuation of study interventions. • TEAEs leading to death.

Death	Counts and percentages.
Changes in laboratory measurements	Summary statistics and boxplots. Laboratory results will also be classified by Grade according to NCI-CTCAE. Worst on-treatment grades as well as shifts to worst on treatment grades will be summarized. Measurements without NCI-CTCAE grading will be summarized by above, within and below normal limits.

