#### Software

All analyses will be performed using SAS® Software version 9.4 or higher or R ([www.r-project.org](http://www.r-project.org)), Version 3.5.1 or higher.

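### The frequentist MTD analysis relies on a convergence flag that can miss separated DLT data, so confidence limits set by the software's stopping tolerance may be tabulated

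*SAP*

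**What the plan says.** Protocol section 9.4.2 (Table 17) plans, beside the Bayesian DLT analysis, a "Sensitivity analysis using frequentist modeling (without prior"). SAP section 15.1, under Frequentist MTD suggestion, makes this a logistic regression with "intercept and slope over log of the scaled dose, no prior". Its steps are:

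- "The dose with targeted toxicity probability of 30% will be identified", and the tested dose just below it becomes the suggested MTD.
- The fitted 30% dose is tabulated with a two-sided 95% confidence interval.
- In addition, "a table will be produced, providing the estimated probability for DLT with a 95% confidence interval, based on the frequentist logistic model".

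The only condition for withholding results is this: "no prior; if the model does not converge, it will be reported as not calculable". No check for separated data, fallback estimator or CI method is given. On implementation, the SAP says that "the program code for this analysis can be found in the TLF shells"; those shells are not among the documents. The general software statement reads "All analyses will be performed using SAS® Software version 9.4 or higher or R", and no procedure is named for this model.

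**The concern.** A convergence flag says that an algorithm stopped by its own criterion. It does not say that a finite estimate exists. When all DLTs lie at the highest tested dose, the likelihood keeps rising as the slope goes to infinity. The deviance flattens along the way, so a routine that stops on a small change in deviance can stop and report success. The written rule would then let the results through.

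At stake are the 95% CI for the 30% dose and the model-based DLT-probability CIs below the top dose. These are the only prior-free model outputs to set beside the Bayesian result. The Bayesian section of SAP 15.1 has an explicit branch for making no MTD suggestion; the frequentist section has only the convergence condition.

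**Working it through.** The plan gives no numerical result for this analysis, so there is no figure to reproduce.

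**Inputs from the documents.** Dose levels 100, 200, 300, 400 and 600 mg (Protocol 4.1.1); usual cohort size 3 (Protocol 6.6.1); at least 6 participants at the MTD or RDE (Protocol 4.1.1); reference dose 800 mg (Protocol Appendix 12; the scaling does not affect whether an estimate exists).

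**Assumptions.** The DLT counts and DLT rates are hypothetical. The CI for the 30% dose uses the delta method on log dose, because the SAP names no method.

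**Step 1: no finite estimate.** Let the top dose have k DLTs in n participants, with none below. Any curve through k/n at the top dose improves as its slope b increases, because the fitted risk at lower doses falls towards 0. The log-likelihood approaches k·log(k/n) + (n−k)·log(1−k/n) but never reaches it. With no DLT anywhere, the intercept a goes to minus infinity instead.

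**Step 2: what the software reports.** The 30% dose is 800·exp[(logit 0.30 − a)/b], with logit 0.30 = −0.847. For 0/3, 0/3, 0/3, 0/6, 2/6 at 100 to 600 mg, iteratively reweighted least squares as in R's glm reports convergence at every tolerance shown:

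| Tolerance | Slope (SE) | 30% dose, mg | 95% CI, mg |
|---|---|---|---|
| 1e-4 | 34.7 (975) | 597 | 465 to 767 |
| 1e-6 | 47.0 (11,900) | 598 | 118 to 3,036 |
| 1e-8 (R default) | 56.9 (87,700) | 598 | 0.16 to 2.2 million |

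At 1e-8, a = 15.67 and b = 56.87, so 800·exp[(−0.847 − 15.67)/56.87] = 598 mg. The interval is set by the stopping rule. The same data entered one row per participant also converge, with slope 48.3 and SE 15,299. The fitted DLT probability at 400 mg is 0.000 with CI 0 to 1. At 600 mg it is 0.33 (0.08 to 0.73), which is usable.

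**Step 3: the point estimate and suggested MTD.** Because the curve passes through k/n at the top dose, the 30% dose equals top dose × exp[(logit 0.30 − logit(k/n))/b]. This tends to the top dose as b grows. It lies just above if k/n is below 30% and just below if k/n is above 30%. At tolerance 1e-8, with convergence reported throughout:

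| DLTs at 600 mg | 30% dose, mg | Suggested MTD, mg |
|---|---|---|
| 0/6 | about 10^-29 | none (no tested dose is lower) |
| 1/6 | 608 | 600 |
| 2/6 | 598 | 400 |
| 3/6 | 592 | 400 |
| 4/6 | 585 | 400 |

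**Step 4: dependence on the routine.** Seven separated hypothetical data sets were fitted (six with DLTs only at the top dose, one with none). Reweighted least squares, a standard GLM fit and BFGS reported convergence in all seven. Newton's method reported non-convergence in six, so there the SAP rule would have worked. SAS was not run. A non-separated set (0/3, 0/3, 1/6, 2/6 at 100 to 400 mg) gave slope 4.40 and a 30% dose of 378.5 mg (274 to 523) with every routine and tolerance.

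**Step 5: how often.** With fixed n = 3, 3, 6, 6 at 100 to 400 mg, the chance of no DLT below the top dose is the product of (1−p)^n over the lower doses. For 3/8/15/30% it is 0.97³ × 0.92³ × 0.85⁶ = 0.27. Multiplying by 0.70⁶ = 0.118 gives 0.03 for no DLT at all, which leaves 0.24 for DLTs only at the top.

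| Assumed DLT rates | Only at top dose | No DLT | Either |
|---|---|---|---|
| 5/12/20/30% | 0.14 | 0.02 | 0.15 |
| 3/8/15/30% | 0.24 | 0.03 | 0.27 |
| 1/3/8/30% | 0.47 | 0.06 | 0.54 |
| 1/2/4/8% | 0.28 | 0.43 | 0.72 |

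**The case against.** Four counter-arguments carry weight.

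- **The code is unseen.** A reader might infer that the convergence check is bound to miss separation. The documents do not show that. The routine sits in the TLF shells, and Newton's method did flag most of the cases tried. R also warns of fitted probabilities of 0 or 1. What remains is that the written rule turns on convergence, not on warnings, and its result should not depend on the routine.
- **The suggested MTD is not distorted when DLTs occur only at the top dose.** A reader might infer that the fitted 30% dose is always meaningless. Step 3 shows otherwise: it follows whether the observed top-dose proportion exceeds 30%. Only the no-DLT case gives a meaningless dose.
- **Absurd limits are easily recognised.** This is true of 0.16 mg to 2.2 million mg. It is not true of 465 to 767 mg, which comes from the same data at a looser tolerance and looks credible.
- **The consequences are limited.** The SAP treats all tests as exploratory and calls this a second approach. The SMC defines the MTD (Protocol 9.4.2.1). SAP 15.1 forwards the Bayesian suggestion to the SMC and states no such step for the frequentist one. Observed DLT counts and percentages per dose level are tabulated anyway, so a prior-free display exists.

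A reader might also infer that this is the most typical data pattern. That cannot be established. Escalation follows a loss-minimising Bayesian model with a redacted prior, and its recommendations do not bind the SMC, so the true frequency cannot be simulated from the documents.

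**Conclusion.** The point holds in a limited form. The SAP's single safeguard can pass data for which no finite estimate exists, including with R's default fit, and R is software the SAP allows. The 95% CI for the 30% dose and the DLT-probability CIs below the top dose would then be set by the stopping tolerance. With no DLTs the 30% dose has no meaning either. When DLTs fall only at the top dose, the 30% dose and the suggested MTD are stable, and the top-dose DLT probability is usable.

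The pattern is realistic for a small escalation. Under the assumed rates and fixed allocation, 15% to 72% of trials would have DLTs only at the top dose or none at all. That range illustrates the risk and does not predict this trial. The size of the CI artefact rests on the assumed counts and the delta-method interval. The non-existence of the estimate rests on neither. The cost of leaving the rule as it is would be a misleading supporting table, with no direct effect on the choice of dose.

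**What to change.** In SAP 15.1, replace the non-convergence condition with a check on the data. Treat the model as not calculable in any of these cases:

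- there is no DLT;
- no DLT occurs below the highest tested dose;
- the data are otherwise separated, meaning that the lowest dose with a DLT is at or above the highest dose with a DLT-free participant, or the reverse ordering holds (for example, DLTs only at the lowest dose).

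Then report the fitted 30% dose, its CI, the model-based DLT-probability CIs and the frequentist MTD as not calculable. Show instead the observed DLT proportion per dose with exact CIs, for example 2/6 = 33% (4% to 78%) and 0/6 = 0% (0% to 46%). State the CI method for the cases where the model is fitted.

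A Firth fit with profile-likelihood CIs may be added as a labelled supplement. In the 2/6 example it gives a 30% dose of 580 mg and a DLT probability at 400 mg of 0.09 (0.001 to 0.31). It should not replace the prespecified fit: its penalty acts as a Jeffreys prior, while the protocol asks for modelling without one. With 1/6 at 600 mg it extrapolates to 1354 mg, more than twice the top tested dose.

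The cost is a few lines of SAP text and code, with no change to trial conduct. The stable suggested MTD is given up when DLTs occur only at the top dose. Little is lost, since it only restates whether the top-dose proportion exceeds 30%.

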## 15.2 Adverse Events

Adverse Events (AE) will be analyzed among the Safety analysis set and presented by dose level (and regimen if different regimens are tested) and overall, and by study part, if not otherwise specified.

### Part 1A:

Treatment-emergent adverse events (TEAEs) are those events with onset or worsening dates occurring within the on-treatment periods as defined in Section 9.7.

This also includes AEs ongoing at baseline, which first improve under study intervention and then worsen irrespective of baseline. Adverse events with changes in toxicity grade/severity, seriousness or outcome of AEs are recorded as separate entries in the eCRF with associated end and start dates (start date equals end date of previous entry, supported in eCRF v8.4 by

‘AECHGID’ in SUPPAE). Records of the same AE will be considered as one event in the analysis. If the severity of the reported event worsens after start of treatment, the TEAE flag will be re-evaluated for the worse and the subsequent records as per the TEAE definition. If the worse record starts outside of the on-treatment period, it will not appear on the summaries/listings of TEAEs, unless otherwise specified. These events will be kept as separate records in the database in order to maintain the full detailed history of the events. The overall outcome of the adverse event is the outcome of the last event in the sequence. When such AEs are listed, start, end date and outcome should be provided together with change date, toxicity grade/severity and seriousness per episode.

Adverse events related to study intervention are those events with relationship missing, unknown or yes.

#### **Part 1B- Cross-over design:**

Treatment-emergent AEs (TEAEs) are those events with onset dates on or after the first administration of study intervention in the first food effect assessment period. Any AE occurring before the administration of study intervention on Day 1 of the first food effect assessment period and resolved before administration of study intervention or not worsening after administration of study intervention in the first food effect assessment period will be included in the AE listings, but will not be included in the summary tables (unless otherwise stated). These will be referred to as “pre-treatment” AEs. An AE occurring after administration of study intervention will be counted towards the last treatment received before the onset, even if the event is not resolved at the beginning of the following food effect assessment period. An AE that worsens during a later food effect assessment period will be counted towards both treatments.

In case AE-related dates are partial, the available information will be used in a conservative approach to determine whether the AE is treatment-emergent. All analyses described in Section 15.2 will be based on TEAEs if not otherwise specified. The AE listings will include all AEs (whether treatment-emergent or not). AEs outside the on-treatment period will be flagged in the listings.

Unless otherwise specified, TEAEs will be summarized by number and percentage of participants with the TEAE in the category of interest by primary System Organ Class (SOC) and Preferred Term (PT) in alphabetic order.

Each participant will be counted only once within each SOC or PT. If a participant experiences more than one AE within a SOC or PT for the same summary period, only the AE with the strongest relationship or the worst severity, as appropriate, will be included in the summaries of relationship and severity.

#### **15.2.1 All Adverse Events**

Adverse Event information is collected on the “Adverse Events Details” eCRF page.

Adverse events will be summarized by worst severity (according to NCI-CTCAE version 5.0) per participant, using the latest version of MedDRA preferred term (PT) as event category and MedDRA primary system organ class (SOC).

If a qualifying AE is reported for a given participant more than once during study intervention, the worst toxicity and the worst relationship to study intervention will be tabulated. In case a participant had events with missing and non-missing grades, the maximum of the non-missing grades will be displayed. No imputation of missing grades will be performed.

Incomplete AE-related dates will be handled as specified in Section 9.9.

The following tables will be created, split by dose level and overall, and by study part:

- The number and percentage of participants with:
  - Any TEAEs
  - Any TEAEs by worst NCI-CTCAE severity grade ( $\geq 3, \geq 4$ )
  - Any M4076 related TEAEs
  - Any M4076 related TEAEs by worst NCI-CTCAE severity grade ( $\geq 3, \geq 4$ )
  - Any M4076 related TEAEs leading to permanent discontinuation of study intervention
  - Any Serious TEAEs
  - Any non-serious TEAEs
  - Any related serious TEAEs
  - Any treatment-emergent AE of special interest (AESI) Cytopenia (as reported in the eCRF)
  - Any treatment-emergent AESI Cytopenia by worst NCI-CTCAE severity grade ( $\geq 3, \geq 4$ ) (as reported in the eCRF)
  - Any TEAEs leading to death (AEs with Grade 5 or outcome “fatal” if grade 5 not applicable)
  - Any related TEAEs leading to death

In addition, all AEs will be tabulated by dose level and regimen (if different regimens tested) and overall and presented by PT and primary SOC in alphabetical order.

For Part 1B the following tables will be created in addition, split by dietary status (“Fed” and “Fasted”) and overall:

- The number and percentage of participants with at least one TEAE by worst NCI-CTCAE severity grade (any grade vs. Grade  $\geq 3$ ), SOC and PT.

A horizontal mirror bar chart will be produced to display TEAEs by worst NCI-CTCAE severity grade. The figure will be split into two time periods (TEAEs occurring during Period 1 vs. TEAEs occurring on or after Period  $\geq 2$ ). AE preferred terms will be displayed along the vertical axis and the absolute number of participants with an AE in each preferred term will be displayed on the horizontal axis. The horizontal axis will be split by time (Period 1 vs. Period  $\geq 2$ ), with incidence of 0 in the center of the axis. Any TEAEs with start date during Period 1 will be displayed on the left side of the mirror plot and any TEAEs with start date on or after Period 2 will be displayed on the right side of the mirror plot. The worst grade will always be displayed, i.e. in case a change in grade occurs within a specified time period, the worst grade will be displayed. Events that occurred

in Period 1 and continued to Period  $\geq 2$  will be displayed on both time periods. If an event improves during Period 1 but continues to Period  $\geq 2$ , this event will only be displayed at the left side of the mirror plot (Period 1).

Display of NCI-CTC severity grade will also differ in color. Within each bar, incidence of TEAEs of toxicity Grades 3 to 5 will be shown in a darker shade and TEAEs of toxicity Grades 1 to 2 will be displayed in a lighter shade. Only TEAEs occurring in at least two participants or with frequency higher than 10% across all dose levels, whichever is greater, will be included in the figure. Preferred terms will be sorted in order of descending frequency of incidence among participants in Period 1.

A listing of all AEs (whether treatment-emergent or not) will be provided. This listing will be sorted by study part, dose level and participant. This listing will additionally contain age, sex, site of primary tumor, SOC, PT, verbatim, CTCAE grade, SAE (yes/no), DLT per investigator (yes/no), DLT per SMC, relatedness to M4076 (yes/no), start date (+treatment day), stop date (+treatment day), duration (in days), action taken with M4076, if treatment was stopped before start of AE: days since stop of treatment, and outcome.

Similarly, a listing of all adverse events Grade  $\geq 3$  (including non TEAEs) will be provided.

### **15.2.2 Adverse Events Leading to Discontinuation, Interruption or Dose Reduction of Study Intervention**

The frequency (number and percentage) of participants with each of the following will be presented in a summary table:

- Any TEAEs leading to temporary discontinuation of M4076
- Any related TEAEs leading to temporary discontinuation of M4076
- Any TEAEs leading to permanent discontinuation of M4076
- Any related TEAEs leading to permanent discontinuation of M4076
- Any TEAEs leading to dose reduction of M4076\*
- Any related TEAEs leading to dose reduction of M4076\*

All TEAEs will be tabulated by dose level and total in a table displaying in separate columns and showing the incidence of TEAEs by SOC and PT (both sorted alphabetically). A listing of TEAEs leading to treatment discontinuation, interruption, or dose reduction of study intervention will be provided. This listing, sorted by study part, dose level and participant, will also include age, sex, site of primary tumor, SOC, PT, verbatim, CTCAE grade, SAE (yes/no), DLT per investigator (yes/no), DLT per SMC, relatedness to M4076 (yes/no), start date (+treatment day), stop date (+treatment day), duration (in days), action taken with M4076, outcome, if treatment was stopped before start of AE: days since stop of treatment, and outcome.

\* Note, dose reduction here is as a response to the eCRF AE page item “Action(s) taken with M4076”.

## 15.3 Deaths, Other Serious Adverse Events, and Other Significant Adverse Events

### 15.3.1 Deaths

All deaths, deaths within 30 days after last dose of study intervention, death within 60 days after first dose, as well as reason for death until end of study, will be tabulated based on information from the “Death” and “Survival Follow-Up” CRFs.

- Number of Deaths
- Number of Deaths within 30 days after last dose of M4076
- Number of Deaths within 60 days after first dose of M4076
- Primary Reason of Death
  - Progressive disease and/or disease related condition
  - Event unrelated to M4076
  - Event related to M4076
  - Unknown

In addition, a listing of Deaths will be provided, defined as any AE with Grade 5, or outcome “fatal” if grade 5 not applicable. This will be sorted by study part, dose level and participant. This listing will additionally contain age, sex, site of primary tumor, SOC, PT, verbatim, CTCAE grade, SAE (yes/no), DLT per investigator (yes/no), DLT per SMC, relatedness to M4076 (yes/no), start date (+treatment day), stop date (+treatment day), duration (in days), action taken with M4076, if treatment was stopped before start of AE: days since stop of treatment, outcome, as well as a flag for death within 30 days of last dose of study intervention and a flag for death within 60 days of first dose of study intervention.

